## 2 FLOW CHARTS

[figure not shown]
### 2.1 GRAPHICAL STUDY DESIGN

#### Graphical study design

## 2.2 STUDY FLOW CHART

Study flow chart of the prospective cohort

## 4 LIST OF ABBREVIATIONS

advCSCC	advanced cutaneous Squamous Cell Carcinoma
AE	Adverse event
BCC	Basal cell carcinoma
BSC	Best supportive care
CR	Complete response
CRF	Case report form
cCRF	electronic Case report form
CRO	Clinical research organization
CSCC	Cutaneous squamous cell carcinoma
DOR	Duration of response
DOT	Duration of treatment
DSD	Disease specific death rate
EC	Ethics Committee
ECOG	Eastern Cooperative Oncology Group
EORTC	European Organization for Research and Treatment of Cancer
H&N	Head and neck
ICF	Informed consent form
irAE	Immune related adverse event
ladvCSCC	locally advanced cutaneous squamous cell carcinoma
LOT	line of therapy
mCSCC	metastasized cutaneous squamous cell carcinoma
NIS	Non-interventional study
NMSC	Non-melanoma skin cancer
ORR	Objective response rate
OS	Overall survival
PD	Progressive disease
PR	Partial response
QLQ	Quality of life questionnaire
QoL	Quality of life
Regeneron	Regeneron Pharmaceuticals, Inc.
SAE	Serious adverse event
SAP	Statistical analysis plan
SCI	Skin Cancer Index
SD	Stable disease
SmPC	Summary of product characteristics
SoC	Standard of care
TTNT	Time to next treatment
TTTF	Time to treatment failure

## 5 INTRODUCTION AND RATIONALE

### 5.1 INTRODUCTION

Nonmelanoma skin cancer (NMSC) is the most common malignancy worldwide, consisting primarily of basal cell carcinoma (BCC) and cutaneous squamous cell carcinoma (CSCC). CSCC makes approximately 20% of all NMSC cases (Stratigos A, 2015). CSCC is generally more aggressive than BCC, with a higher likelihood of becoming ladvCSCC or mCSCC (Rogers HW, 2010). The exact incidence of CSCC is unknown, as registries do not track all cases. However, the lifetime risk for developing CSCC is estimated to be 7%–11%, with dramatic observed increases over recent decades (Miller DL, 1994).

About 16,881 new cases in men and 14,855 cases in women of CSCC were estimated in Germany 2013 (40 / 100,000 people per year resulting in 32,000 CSCC patients annually) (Leiter U, 2014). A high incidence rate is also found in Switzerland (28.9 / 100,000 person per year) (Hollestein LM, 2012; Xiang F, 2014). Although overall CSCC incidence is common, only a small percentage of approx. 5% is expected to progress to mCSCC or ladvCSCC. The majority of CSCC patients can be managed with local therapies (Lippman SM, 1992). The remaining 5% of patients are at high-risk for locally advanced disease and metastasized CSCC. The estimated five-year rate of CSCC recurrence is 8% (Stratigos A, 2015; Levine DE, 2015; Thompson AK, 2016). Larger primary lesions (> 2 cm in diameter), higher histologic grade, particularly thicker lesions, and immune suppressed individuals are considered to be at higher risk for metastasis, with occurrence estimated between 2–5% of patients (Stratigos A, 2015; Thompson AK, 2016). The CSCC lethality rate is difficult to estimate in part due to inaccurate incidence estimates. In Australia the estimated mortality rate is approximately 5%, whereas U.S. studies suggest a rate of 1% (Joseph MG, 1992; Clayman GL, 2005). No standard treatment regimen for advCSCC (mCSCC or ladvCSCC) has been established and tumors are often managed similarly to head and neck SCC. Therefore, patients with advanced disease have a poor survival prognosis. In general, the approach to management relies on surgically removing “satellite or in-transit” metastases around the primary tumor if complete removal is possible. In those with unresectable CSCC, treatment is difficult. A partial response was shown in 44% and a SD in 24% of patients with previously available therapies (Jarkowski et al. 2016). The evidence for effectiveness of currently available systemic therapies for advCSCC is limited to case studies and phase 2 studies with low patient numbers. Generally, advCSCC is chemo responsive; but responses are usually very short-lived and connected to high toxicity, especially in the predominantly elderly patient population.

Radiation therapy alone or in combination with chemotherapy may be used as an alternative option when surgery is not feasible (Stratigos A, 2015). With limited survival, advCSCC (mCSCC and ladvCSCC) have a high unmet medical need (Karia PS, 2013).

## Evidence for Cemiplimab in advCSCC

Substantial progress has recently been made in the development of immunotherapy for the treatment of cancer and specifically advCSCC. Checkpoint-blockade uses antibodies that impede immune inhibitory pathways such as programmed cell death 1 (PD-1) or PD-1 ligand 1 (PD-L1) interaction (Chang ALS, 2016). Efforts to characterize the genetic landscape of CSCC have been hampered by very high background mutation rates associated with UV damage which can be 5 to 15 times higher than what is found for non-cutaneous tumors. And with understanding the genomic signatures of aggressive CSCC it provides an opportunity to intensify upfront therapies in order to prevent the morbid consequences of treating advanced disease (Pickering 2014).

Cemiplimab is a high affinity, fully humanized, hinge stabilized IgG4P antibody against the PD-1 receptor that blocks the interaction of PD-1 with its ligands, PD-L1 and PD-L2 (Migden MR, 2018). Cemiplimab was approved by the FDA (Sep/2018) and by the EMA (June 28th 2019) for the treatment of adult patients with advCSCC who are no candidates for curative surgery or curative radiation [SmPC, Fachinformation LIBTAYO (Cemiplimab), September 2019], and is being studied in several other indications.

The efficacy of Cemiplimab in patients with mCSCC (nodal or distant) or ladvCSCC who were not candidates for curative surgery or curative radiation was evaluated in two open label, multicenter, non-randomized, multicohort studies: Study 1423 (NCT012383212) and 1540 (NCT01760498) (Kaplun H 2018, Papadopoulos KP 2016). Patients received Cemiplimab 3 mg/kg intravenously every 2 weeks for up to 48 weeks in study 1423 and up to 96 weeks in study 1540. In study 1540 one group with mCSCC patients were treated with a fix dose of 350mg every 3 weeks. The major efficacy outcome measure was confirmed by ORR. The efficacy analysis was conducted when all patients had the opportunity for at least 6 months of follow up. At the time of data cut-off (October 27th 2017) 47% of patients with mCSCC showed an objective response to Cemiplimab in study 1540, with a mean observed time to response of 1.9 months. The ORR in 76 locally advCSCC was 43.6% (data cut-off October 10th 2018) (Migden et al., ASCO 2019). At the time of data cut-off (September 20th 2018) PFS was 18.4 months in 59 mCSCC treated with cemiplimab (Guminski et al., ASCO 2019).

## 5.2 RATIONALE

Given the drastic shift in the therapy options for advCSCC with the approval of Cemiplimab for the treatment of mCSCC and ladvCSCC, it is important to gain a better understanding of the changing paradigms in treatment of these patients. Gathering data in the time-frame before and after the approval of Cemiplimab for the therapy of advCSCC will allow for an assessment of therapy outcomes in a real-world setting.

Therefore, via this longitudinal two-cohort study with a prospective and a retrospective cohort, we will characterize patients and disease characteristics, survivorship, real-world treatment patterns and clinical outcomes among adult patients diagnosed with advCSCC (mCSCC and ladvCSCC).

## 6 STUDY OBJECTIVES

The principal objective of the Cemiplimab NIS with two cohorts is to examine real-world data of advCSCC patients undergoing treatment with Cemiplimab to identify potential determinants of disease progression, QoL, and other health related outcomes for advCSCC patients in a real-world setting.

The objective of this NIS is to collect and describe long-term effectiveness and safety of treatment with Cemiplimab.

### Primary objectives

*Prospective and retrospective cohort:* Primary objective for this Cemiplimab NIS is to evaluate the clinical outcomes in treatment of advCSCC as a result of TTNT. Assessments of the response are clinical observations of physician's choice.

### Secondary objectives of the prospective cohort

- DOR to identify and describe long-term effects of treatment of patients with CSCC
- DCR (CR+PR+SD) at 3, 6, 9, 12, 18, 24, 36 months
- To assess patient experience, functional status, QoL and pain, in a real-world setting for patients with advCSCC at 3, 6, 9, 12, 18, 24 and 36 months
- To collect and describe safety data on study participants
- To describe patients who receive Cemiplimab as treatment for advCSCC in a real-world setting
- OS defined as duration from current mCSCC or ladvCSCC diagnosis and also from the initiation of each LOT until death or end of follow up
- Proportion of patients surviving at month 3, 6, 9, 12, 18, 24 and up to months 36 from initiation of systemic therapy
- PFS defined as time from first documented systemic cemiplimab therapy initiation until progression or treatment discontinuation due death or end of follow up
- Patient demographics and baseline characteristics (incl. age, performance status etc.) at study entry
- Characterization of Cemiplimab usage patterns
- Cemiplimab treatment regimen (initial dose and date of initiation and regimen changes)
- Treatment prior to and post Cemiplimab treatment, incl. surgery, radiation, systemic therapies incl. agents administered, dose, frequency and duration

- Surgery post initiation of Cemiplimab treatment
- DOT
- TNM stage (AJCC or UICC)
- Analysis of Cemiplimab tolerability and safety profile in daily clinical practice
- Observed rates, reasons and timing of the discontinuation of Cemiplimab
- TTF including lack of response and discontinuation due to AE
- Analysis of change in patient reported QoL as per EORTC-QLQ-C30 QoL questionnaire during treatment with Cemiplimab (for prospective cohort only)

### **Secondary objectives of the retrospective cohort**

- Description of retrospective patient population, patterns of care and effectiveness of different treatment options used under routine conditions for advanced CSCC prior to Cemiplimab launch
- To collect and describe safety data on study participants
- Proportion of patients surviving at month 3, 6, 9, 12, 18, 24 and up to months 36 from initiation of systemic therapy
- PFS defined as time from first documented systemic therapy initiation until progression or treatment discontinuation due death or end of follow up
- Patient demographics and baseline characteristics (incl. age, performance status etc.) at study entry
- TNM stage (AJCC or UICC)
- Patterns of treatment for the retrospective cohort.

## 7 STUDY DESIGN

### 7.1 DESCRIPTION OF THE STUDY DESIGN

This is an observational study with two cohorts (prospective and retrospective) of adult patients with advCSCC. No study intervention will be performed. It is an international multicenter study of Germany, Austria and Switzerland.

#### **Prospective cohort:**

Each patient will be initially treated with Cemiplimab and documented during a follow up time of 36 months. Documentation will be performed up to 8 times (D1: Baseline, D2: after approx. 3 months, D3: after approx. 6 months, D4: after approx. 9 months, D5: after approx. 12 months, D6: after approx. 18 months, D7: after approx. 24 months, D8: after approx. 36 months / End of the Study). In case of Cemiplimab treatment discontinuation at any time, the documentation will continue until D8 or patient's death to assess outcome and further therapeutic modalities.

The prospective cohort of this observational study plans to collect patients with mCSCC – defined as patients with local/regional (nodal metastasis, field cancerization ect.) as well as distant metastasis (also distant lymph-node), and advCSCC – defined as patients that could not be cured either by curative surgery, curative radiotherapy or both based on a decision of an interdisciplinary tumor board. These patients will receive treatment with Cemiplimab within their clinical routine treatment.

At each participating study site, all advCSCC patients who will initiate treatment with Cemiplimab in a real-world setting will be eligible to participate in the study until the enrollment goal is achieved. The decision to prescribe Cemiplimab will be based solely on the treating physician's clinical judgment. Patients who meet inclusion criteria according to SmPC of Cemiplimab and have signed the ICF will be included in the study.

#### **Retrospective cohort:**

Patients first diagnosed with advCSCC between Jan/2012 and Aug/2019 will be included and documented at study entry with anonymous data.

#### **Informed Consent Form (ICF)**

It is the responsibility of the physician or designee to obtain written ICF from each compliant patient of the prospective cohort prior to the documentation of his / her data in the eCRF. One original ICF must be retained by the study site as part of the patient's study record, and another original of the signed ICF must be given to the patient. The ICF must be provided before the patients data are documented in the eCRF.

Enrolled patients who initiate treatment with Cemiplimab will complete baseline QoL assessments at the time of ICF, and will continue with subsequent assessments at their Cemiplimab dosing and advCSCC standard of care (SoC) visits for up to 3 years. Additional procedures will be performed as dictated by the local SoC, as deemed necessary by the treating physician based on usual care. Data collection will mirror SoC procedures relating to the patient's treatment. Patients will remain eligible and will be encouraged to stay in the study if they discontinue Cemiplimab (permanently or temporarily). Once enrolled, patients will remain in the study until further participation is declined.

In the study the data to support the primary objectives are abstracted from medical records for patients with advCSCC (ladvCSCC or mCSCC), living or deceased, from the time of advCSCC diagnosis (i.e., index date) until the most recently documented visit, death, or lost to follow up whichever comes later. Specifically, data on treatment patterns prior to date of first mCSCC or ladvCSCC diagnosis, as far as data permits will be collected to support the secondary objectives.

## **7.2 DURATION OF STUDY PARTICIPATION FOR EACH PATIENT**

In the prospective cohort the data will be recorded during a follow-up of 36 months, beginning after study inclusion.

In the retrospective cohort we will document at one time point patients not intended for Cemiplimab therapy, who were first diagnosed advCSCC between Jan/2012 and Aug/2019. QoL data will be collected from patients within the prospective cohort. It is planned to perform yearly interim analyses and a final report at the end of the study.

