## 1 SYNOPSIS

COMPOUND: Cemiplimab (SAR439684)	
STUDY No: OBS16381	
TITLE	Two cohort registry study for patients with advanced CSCC treated with Cemiplimab or other approaches
LOCATION	Approx. 60 sites in Germany, plus 5 sites in Switzerland and 5 sites in Austria
SCIENTIFIC COMMITTEE CHAIR PERSON	[REDACTED]
STUDY OBJECTIVE(S)	
The objectives of the study are
 
Prospective cohort:
 

• To identify TTNT

• To identify potential determinants of disease progression as final outcome, Quality of life (QoL), pain and other health related outcomes for CSCC patients undergoing treatment with Cemiplimab

• To collect long-term effectiveness and describe effects of treatment

• To collect safety data in a real world setting

 
Retrospective cohort:
 

• To examine real-world data of advanced CSCC (advCSCC) patients who were treated before approval of Cemiplimab (treatment approaches, safety, patient characteristics, long-term effects)

 
Primary objective prospective and retrospective cohort:
 
Primary objective for this non-interventional study (NIS) is time to next treatment (TTNT) excluding best supportive care (BSC).
 
Secondary objectives prospective cohort:
 
Patient demographics and baseline characteristics (TNM stage), Cemiplimab treatment regimen, duration of treatment (DOT), prior and post Cemiplimab treatments, response to Cemiplimab treatment (ORR, CR, PR, SD), duration of response (DOR), disease control rate (DCR = CR+PR+SD), time to treatment failure (TTFT), overall survival (OS), progression free survival (PFS), safety data, quality of Life (QoL) incl. pain.
 
Secondary objectives retrospective cohort:
 
Patient demographics and baseline characteristics (TNM stage), effectiveness (ORR, PFS, OS) and safety of different treatment options used routinely for advanced CSCC prior to Cemiplimab launch, patterns

	of treatment.

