STUDY DESIGN & DURATION	
This is a non-interventional multicenter study in Germany, Austria and Switzerland. The study includes two cohorts of adult patients with advCSCC who receive either treatment with Cemiplimab (prospective cohort) or other therapeutic approaches (retrospective cohort).
 
Enrollment will take place at approx. 70 study sites. The selection of participating sites will attempt to capture a representative sample of advCSCC treating clinic and office based physicians to get data from a real world setting outside of clinical trials.
 
In each cohort 200 patients will be enrolled from Germany, Austria and Switzerland. The duration of follow up will be up to 36 months for each patient in the prospective cohort.
 
Patients who meet the inclusion criteria and have signed the informed consent form (Sanofi-ICF) (only in the prospective cohort) will be included in the study.

STUDY POPULATION	
Inclusion Criteria
 
For the prospective cohort:
 
 
a. Planned treatment with Cemiplimab for advCSCC according to SmPC
 
b. Able to understand and complete study-related questionnaires
 
c. Signed ICF
 
 
For the retrospective cohort:
 
 
d. Patients <math>\geq</math> 18 years with first diagnosed advCSCC (locally advanced or metastatic CSCC) between Jan/2012 and Aug/2019
 
e. From these patients only anonymous data will be collected. Thus no Sanofi-ICF is needed This procedure allows including data from patients who are no longer alive (planned).
 
 
Exclusion Criteria
 
For the prospective cohort:
 
 
a. Missing ICF
 
b. advCSCC of unknown primary origin
 
c. Any condition that, in the opinion of the study physician, may interfere with patient's ability to participate in the study, such as severe cognitive impairment or other comorbidities that would, in the opinion of the study physician, predictably prevent the patient from adequately completing QoL assessments.
 

	
For the retrospective cohort:
 
 
d. Patients enrolled in clinical trials with Cemiplimab for advCSCC treatment
 
e. advCSCC of unknown primary origin
 
 
Sample Size: 400 patients (200 patients in each cohort)

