**Retrospective Cohort:**

In the retrospective cohort this study will document (1 documentation time point) patients not intended for Cemiplimab therapy and first diagnosed with advCSCC between Jan/2012 and Aug/2019. It will obtain data of anti tumor therapies (prior to Cemiplimab approval) and

[figure not shown]
	
their outcome. We plan to document the disease history including prior surgery, radiotherapy, systemic therapies and the related safety data as well as effectiveness. The largest study with advCSCC was recently published (Hillen et al. 2018), which examined retrospectively 190 patients from Germany and Austria first diagnosed between Jan/2010 and Dec/2011 with a first-time follow-up on May/2014.
 
Within this retrospective cohort, we will collect only anonymous data from patients without Sanofi-ICF. This procedure allows including data from patients who are no longer alive (planned)
 
Patient characteristics (age, sex, diseases, immunosuppression, comorbidities, localization, etc.) and therapeutic modalities will be evaluated (as in the prospective cohort if applicable).
																				

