ESTIMATED DURATION OF THE STUDY	
Prospective cohort: Estimated enrollment duration 24 months
 
Estimated dates:
 

○ First Patient In: 01.03.2021

○ Last Patient In: 01.03.2023

○ Last Patient Out: 01.03.2026

 
Retrospective cohort: Patients first diagnosed with advCSCC between Jan/2012 and Aug/2019 and not intended to receive Cemiplimab will be documented in the retrospective cohort once.

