### 8.2 INCLUSION CRITERIA

Prospective cohort:

- Planned treatment for advCSCC adult patients  $\geq 18$  yrs who are at the first time initiated on Cemiplimab treatment according to SmPC of Cemiplimab
- Able to understand and complete study-related questionnaires
- Signed ICF

Retrospective cohort:

- Patients  $\geq$  18 years with advCSCC first diagnosed between Jan/2012 and Aug/2019
- From these patients only anonymous data will be collected. Thus no Sanofi-ICF is needed. This procedure allows including data from patients who are no longer alive (planned).

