### **8.3 EXCLUSION CRITERIA**

Prospective cohort:

- Missing ICF
- advCSCC of unknown primary origin
- Any condition that, in the opinion of the investigator, may interfere with patient's ability to participate in the study, such as severe cognitive impairment or other comorbidities that would, in the opinion of the investigator, predictably limit compliance with the intended treatment plan, or prevent the patient from adequately completing QOL assessments.

Retrospective cohort:

- Patients enrolled in clinical trials for advCSCC treatment
- advCSCC of unknown primary origin

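### Who belongs in the retrospective cohort is defined inconsistently, and the cemiplimab-intention clause has no time point

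*Protocol*

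**What the plan says.** Three places attach a cemiplimab condition to the retrospective cohort:
- Section 7.2 documents, at one time point, "patients not intended for Cemiplimab therapy, who were first diagnosed advCSCC between Jan/2012 and Aug/2019".
- The synopsis entry on main data collected has "patients not intended for Cemiplimab therapy and first diagnosed with advCSCC between Jan/2012 and Aug/2019".
- The synopsis entry on study duration says that patients "not intended to receive Cemiplimab will be documented in the retrospective cohort once".

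The places that define eligibility do not carry it. Section 8.2 asks for adults "with advCSCC first diagnosed between Jan/2012 and Aug/2019" and nothing about cemiplimab. The synopsis criteria, the cohort description in 7.1 and the exclusions in 8.3 are also silent on it.

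Two further conflicts concern the same cohort:
- **Trial exclusion.** The synopsis excludes "Patients enrolled in clinical trials with Cemiplimab for advCSCC treatment"; section 8.3 excludes "Patients enrolled in clinical trials for advCSCC treatment".
- **Calendar limit.** The synopsis objective is patients "who were treated before approval of Cemiplimab". Section 5.1 dates the EMA approval to 28 June 2019. Eligibility runs on diagnosis date to August 2019, with no limit on when treatment began.

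The prospective criteria in 8.2 require a first cemiplimab initiation. They limit neither the date of diagnosis nor earlier lines of therapy.

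**The concern.** Sites choose their own charts (section 8.4), so two sites following different sections would build different cohorts. The missing time point makes this more than an editorial matter.

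Intention judged at diagnosis would make the clause almost empty, because only about 2 of the 92 months in the diagnosis window follow EMA approval. Section 7.2 places the clause in the sentence about the single documentation, and documentation starts on 01.03.2021. A site could therefore reasonably apply it when it opens the chart. A patient diagnosed in 2017, alive in 2020 and then given cemiplimab would be dropped because of something that happened after time zero.

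If a site follows 8.2/8.3 instead, that patient stays in. A similar patient who first starts cemiplimab after March 2021 could also meet the prospective criteria, and no passage forbids entry into both cohorts.

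At stake are OS and the survival proportions to month 36 in the retrospective cohort, to a lesser degree its TTNT, and the exploratory pooled ORR in 14.3.2.2. Section 5.2 presents the study as data before and after approval, so readers will set the cohorts side by side although no comparison is planned.

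**Working it through.** **Yardstick from the plan.** The synopsis gives 95% CIs for median TTNT with 180 events. The exponential interval 2dM/χ²(0.975; 2d) to 2dM/χ²(0.025; 2d), with d = 180, gives 26.1–34.9 at M = 30 (width 8.9), 34.7–46.6 at 40 (11.8) and 43.4–58.2 at 50 (14.8). The plan's figures reproduce. The half-widths are about 4.4, 5.9 and 7.4 months.

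**Calendar, in months from January 2012.** The diagnosis window is 0 to 92, EMA approval falls at 89.9, start of documentation at 110 (01.03.2021) and last patient in at 134 (01.03.2023).

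**Assumptions not in the protocol.** Diagnosis is uniform over the window, times are exponential from diagnosis, and the shares moving to cemiplimab are as stated below. The results are illustrations, not estimates.

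**OS if the clause is applied at documentation.** With λ = ln 2/median, the share alive at approval is [(1 − e^(−89.9λ))/λ + 2.1]/92. For a median of 24, λ = 0.0289, which gives (32.0 + 2.1)/92 = 0.37. Medians of 12 to 48 give 0.21 to 0.57. Excluding a share q of those alive at approval and re-estimating by Kaplan-Meier, with charts read at month 122, gives:

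| True OS median | q = 0.10 | q = 0.25 | q = 0.50 |
|---|---|---|---|
| 12 | 11.8 | 11.4 | 10.8 |
| 24 | 23.2 | 21.9 | 19.7 |
| 36 | 34.4 | 32.0 | 27.5 |
| 48 | 45.6 | 41.9 | 34.9 |

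Repeat runs differ by about 0.1 month. At a true median of 24, 36-month survival falls from 0.354 to 0.341–0.280. Every entry moves down, because exclusion requires survival past approval.

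**TTNT if the clause is applied at documentation.** Patients are removed if their next therapy falls between approval and chart reading and is cemiplimab. Assumed: 60% of TTNT events are a next therapy, 50–80% of those are cemiplimab, and charts are read between months 110 and 134.

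| True TTNT median | Change in estimated median |
|---|---|
| 12 | to 11.7–11.0 (−3% to −8%) |
| 24 | to 23.6–21.6 (−2% to −10%) |
| 30 | −0.2 to −2.7 months |
| 40 | +0.5 to −2.1 months |
| 50 | +1.6 to −0.3 months |

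At the planned 30–50 months the shift stays below the half-width of the plan's own interval and changes sign. With half of events a next therapy, 25–80% of them cemiplimab and charts read at month 122, the range is −1.2 to +0.9 months.

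**Overlap if the clause is not applied.** Dual eligibility needs a next therapy that is a first cemiplimab course begun between months 110 and 134. At a TTNT median of 40, λ = 0.01733 and the probability of an event in that window is (e^(−18λ) − e^(−110λ) − e^(−42λ) + e^(−134λ))/(92λ) = 0.1986/1.594 = 0.125. Multiplying by 0.5 (next therapy rather than death) and by 0.25–0.80 (cemiplimab) gives 1.6–5.0%, or 3–10 of 200. Medians of 30 and 50 give much the same.

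**Effect on the pooled ORR.** If the two responses of a duplicated patient were perfectly correlated, 10 pairs among 400 records would raise the variance by (380 + 40)/400 = 1.05, so the interval should be √1.05 = 1.025 times as wide. Three pairs give √(406/400) = 1.007.

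**The case against.** The protocol never says that intention is judged later. The synopsis pairs the phrase with therapies given before approval, so it may only describe a pre-cemiplimab comparator. Judged at diagnosis or at the index therapy, it would not depend on the future. This stands: the defect is an undefined time point, and future-dependence is one plausible reading of it.

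A reader might infer that the cohort loses its long survivors and that TTNT is clearly shortened. The documents do not support this. Only survivors who became cemiplimab candidates would leave; durable responders who need no new therapy stay. A simulation without a chart-reading date gives TTNT falls of 11–17% at a median of 24. That is too much, because a switch after the single documentation cannot remove anyone.

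A reader might also infer that duplicates cannot be found. The anonymised database cannot show them, but the site staff who select the charts can.

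Finally, it is tempting to say that both cohorts are biased in the same direction. The ground offered is the prospective exclusion in 8.3 of patients with conditions that would "predictably limit compliance with the intended treatment plan". The synopsis omits that ground, 7.1 opens the study to all patients starting cemiplimab, and section 10 says that compliance with a treatment protocol does not apply. These should be reconciled, but no figure shows a directional effect. The study is descriptive, and TTNT is estimated separately by cohort.

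**Conclusion.** The concern holds as a contradiction about membership, with consequences that depend on how it is resolved. The cemiplimab clause, the trial exclusion and the calendar limit each differ between parts of the protocol.

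If the clause is applied at documentation, the firm consequence is a downward bias in retrospective OS and survival proportions. Its size rests on the assumed OS median and the assumed share excluded. A substantial bias in the primary TTNT at the planned medians is not shown. If the clause is not applied, overlap is possible, involves few patients and widens the proper pooled ORR interval by at most about 2.5% under these assumptions.

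The point should be corrected because the cohort's definition must be the same at every site. It does not invalidate the primary analysis.

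**What to change.** 1. Put one retrospective membership rule in 8.2/8.3, the synopsis and 7.2, judged at baseline: the index anti-tumour therapy started before cemiplimab approval or launch and was not cemiplimab. Delete the intention clause wherever it appears and align 7.1.
2. State which approval or launch date applies in each country. The protocol gives the EMA date but none for Switzerland, and uses both approval and launch as the reference.
3. State how patients treated only by surgery or radiotherapy are handled. The synopsis plans to document these treatments, whereas the retrospective PFS and survival proportions start at systemic therapy. Requiring a first systemic therapy would silently drop these patients.
4. Keep patients who later receive cemiplimab and count it as the next systemic therapy in TTNT.
5. Use one wording for the trial exclusion.
6. Have sites record, before anonymisation, whether the patient is also in the prospective cohort, so that the pooled ORR counts each patient once.
7. Reconcile the compliance wording in 8.3 with the synopsis, 7.1 and section 10.

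Cost: an amendment to the wording and one CRF item. Version 2.0 already edited retrospective eligibility as a non-substantial change; whether this one also qualifies is for the sponsor to establish. A few patients first treated after approval would leave the pool, and charts already entered would need a check against the final rule.
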